Intoxication: The study population targets OUD patients, who were actively using illicit opioids prior to the hospitalization. As such, it is possible for participants to be intoxicated from illicit opioids or other substances during their work with recovery coaches or during study visits. Participants will be required to abstain from substances other than buprenorphine for at least 4 hours prior to each study visit. Intoxication will be determined through self-report and clinical observation. If a participant is intoxicated in any way, they will not be permitted to complete the visit, and the visit will be rescheduled at the earliest convenient time. Consistent with standard clinical practice, when possible, the recovery coaches will discuss with the candidate to determine the best management options. This may include notifying the inpatient/outpatient providers or family members, referring to medical treatment, calling emergency services, or escorting the participant to the Emergency Room at Brigham and Women's Hospital.

Overdose: Patients with OUD are at heightened risk from fatal and non-fatal overdoses during and after buprenorphine treatment, especially if using alcohol or sedative drugs such as benzodiazepines. As such, participants will be required to abstain from using these substances. However, given their underlying illness, some participants may still ingest these other substances during the study period. All study staff, including recovery coaches, and all participating subjects will be trained in the recognition and initial management of an overdose using the naloxone-rescue kits. Subjects will also be asked to identify family or supports that can carry the naloxone rescue kits. The candidate is a board certified addiction psychiatrist well versed in the recognition and management of overdoses, and appropriate clinical action will be taken in the event of an overdose. In addition, all recovery coaches will receive training on overdose prevention and the use of naloxone rescue kits.

VIII. Potential benefits:

The risk/benefit ratio for this study is relatively low, primarily because the intervention and the data collection procedures are minimally invasive. An extensive screening procedure will ensure that individuals entering the trial will have no contraindications. Trained research personnel will perform all study procedures to minimize risks, discomforts, and adverse effects. Buprenorphine treatment is a FDA-approved treatment for the treatment of OUD, and reduces illicit opioid use and related morbidities associated with opioid use disorders. The recovery coaching intervention may provide benefit to the study participants by increasing their likelihood of remaining in treatment, reducing their illicit opioid use, and reduce hospital readmissions.

This study will generate valuable information about the effect of combining recovery coaches with buprenorphine initiated during hospitalization. The results will help inform the direction needed to take in developing effective strategies to improve the care of hospitalized OUD patients. Given the potential public health impact, and the minimal risk associated with participation, we believe that the risk to participants is reasonable.

IX. Monitoring and quality assurance:

1. Data Quality and Management

- a. Description of plan for data quality and management: The PI or study staff will review all data collection forms on an ongoing basis for data completeness and accuracy as well as protocol. To minimize any conflicts of interest, a physician from Brigham and Women's Hospital familiar with clinical research who is not a collaborator or investigator on the proposed project, nor a close colleague, will serve as an independent individual to monitor the data and safety.
- b. Frequency of review: The candidate will complete reports every 3 months detailing the study progress and subjects' status, any adverse events, and any protocol deviations, which will be submitted to the independent individual for review.

2. Subject Accrual and Compliance

- a. Measurement and Reporting of Subject Accrual, Compliance with inclusion/exclusion criteria: Review of the rate of subject accrual and compliance with inclusion/exclusion criteria will occur every 3 months to ensure that a sufficient number of participants are being enrolled and that they meet eligibility criteria and the targeted ethnic diversity goals outlined in the proposal.
- b. Measurement and reporting of participant adherence to treatment protocol: Data on adherence to the treatment protocol will be collected weekly by research staff and reviewed quarterly by the PI. Fidelity to the treatment manual will be reviewed by the candidate each week with the recovery coaches.

3. Justification of sample size: In a study of a care management intervention for patients with substance use disorder in primary care, individuals receiving the intervention were more likely to remain in treatment at 24 weeks (40% vs 10%). While this study is entirely community based, no other comparable studies have been conducted with OUD patients on buprenorphine. Based on this effect size, we plan to screen 145 participants, assuming a 60% attrition due to screening failure, allowing for a sample size of 58 available for analysis, evenly divided between the control and intervention arm. This will yield a statistical power of 0.8 and 95% confidence level to detect differences in proportions of participants who remain in treatment at 24 weeks, as confirmed by the BWH-affiliated clinic. The study will not be powered to detect smaller effect sizes, but will be helpful in providing important information about effect sizes to adequately power future studies.

4. **Stopping rules:** This study will be stopped prior to its completion if: (1) the intervention is associated with adverse effects that call into question the safety of the intervention; (2) difficulty in study recruitment or retention will significantly impact the ability to evaluate the study endpoints; (3) any new information becomes available during the trial that necessitates stopping the trial; or (4) other situations occur that might warrant stopping the trial
5. **Designation of an independent monitor:** To minimize any conflicts of interest, a physician from Brigham and Women's Hospital familiar with clinical research who is not a collaborator or investigator on the proposed project, nor a close colleague, will serve as an independent individual to monitor the data and safety.

6. **Safety Review Plan:** Study progress and safety will be reviewed monthly (and more frequently if needed). Progress reports, including patient recruitment, retention/attrition, and AEs, will be provided to the Independent Monitor following each of the monthly reviews. An Annual Report will be compiled and will include a list and summary of AEs. In addition, the Annual Report will address (1) whether AE rates are consistent with pre-study assumptions; (2) reason for dropouts from the study; (3) whether all participants met entry criteria; (4) whether continuation of the study is justified on the basis that additional data are needed to accomplish the stated aims of the study; and (5) conditions whereby the study might be terminated prematurely.
7. **Study report outline for the independent monitor:** Study Report tables will be generated only from aggregate (not by group assignment) baseline and aggregate safety data for the study population. A separate Closed Safety Report, with masked group baseline and safety data, will be generated for the Independent Monitor(s) by a designated unmasked member of the team but will not be reviewed by the study team.
8. **Informed consent:** The subject (if applicable, parent/guardian) will be asked to review the study consent form. The PI or Co-Investigator (Co-I) will meet with the subject to review the form, to confirm the subject's understanding of the study, and to answer any questions the subject might have. Once the subject demonstrates understanding of the study and agrees to participate in the study, the consent will be signed in the presence of the PI (or Co-I) and a witness
9. This study does not involve any medications or devices and carries no risk of harm from such medications or devices.

X. References

1. Stein, M. D. Medical consequences of substance abuse. *Psychiatr. Clin. North Am.* **22**, 351–370 (1999).
2. Stein, M. D., O'Sullivan, P. S., Ellis, P., Perrin, H. & Wartenberg, A. Utilization of medical services by drug abusers in detoxification. *J. Subst. Abuse* **5**, 187–193 (1993).
3. Ronan, M. V. & Herzig, S. J. Hospitalizations Related To Opioid Abuse/Dependence And Associated Serious Infections Increased Sharply, 2002-12. *Health Aff. Proj. Hope* **35**, 832–837 (2016).
4. Owens, P. L., Barrett, M. L., Weiss, A. J., Washington, R. E. & Kronick, R. in *Healthcare Cost and Utilization Project (HCUP) Statistical Briefs* (Agency for Health Care Policy and Research (US), 2006).

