Due to the COVID-19 pandemic, and as this is a minimal risk study, we also propose an option for remote consenting for the duration of the public health emergency. As the research assistant will only be allowed on-site for a limited number of days each week, there is a possibility that part of the enrollment or consenting process will have to happen remotely before the subject is discharged. In this case, all preceding recruitment procedures will remain the same; either the primary medical team or the addiction psychiatry team will inform the patient about the study and ask whether the patient consents to be approached by the study team. If the patient consents, the research assistant will introduce the study, answer questions, determine preliminary study eligibility, and allow ample time for the patient to consider whether to enroll. The research assistant will also leave a physical copy of the Research Study Fact Sheet, the informed consent form, and the "Notification of Changes due to COVID-19" general information sheet. These will be for the patient to keep and review in case the research assistant is unable to return for an in-person follow-up to review and sign the consent form, after the patient has had time to consider the study. In the case that enrollment will continue remotely, the research assistant will call the participant to conduct the consent discussion, and then subsequently randomize the participant and conduct the baseline measures remotely via phone. Since this is a minimal risk research study, the remote process would use a verbal consent process which requires waiver of informed consent documentation (no signature will be obtained on the consent document).

A study staff will approach potential participants to determine preliminary study eligibility. Based on prior studies of this population, we expect OUD patients to have the following characteristics: 50% male, 70% Caucasian, 40% with prior heroin use, admission diagnosis of acute pain (40%) and infection (20%), length of stay of 11 days, and 80% needing opioid

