analgesia. At the initial screen, all eligible English-speaking OUD patients will be offered a referral to methadone treatment and informed about the trial. Extended-release naltrexone, which requires that all opioids be stopped 7-10 days prior to initiation, will not be offered because the vast majority of patients screened will have received opioid analgesic during the hospitalization. As such, most potential patients would not be able to initiate naltrexone prior to discharge. Initiation of buprenorphine will be considered for patients who are medically stable enough to undergo induction, have an interest in initiating buprenorphine maintenance treatment, and have no medical or surgical contraindications. The full inclusion and exclusion criteria will then be applied.

V. Study procedures:

Randomization: After informed consent is given, participants will be randomized using a computerized random number generator with numbers in sealed envelopes in study binders.

Interventions:

Control group: Participants in the control arm will receive treatment-as-usual at our hospital. All participants will receive a thorough psychosocial evaluation to help with discharge planning. Following initiation of buprenorphine or methadone, the addiction social worker will provide the participant with the intake number for the BWH-affiliated buprenorphine programs, or contact information for relevant methadone programs. Patient preference due to geographic considerations will be taken into account when choosing the clinic to which participants are

Table 2: Components of the ISTOP intervention
In-hospital component (adapted from MISSION manual)

Session #1: (90 minutes with Recovery Coach)

- 1) Introduce recovery coach, and review overall intervention
- 2) Complete a psychosocial needs assessment
- 3) Create a provisional treatment plan based on identified service needs and prioritizing of goals.
- 4) Refer to BWH/BWFH-affiliated buprenorphine clinic
- 5) Use motivational interviewing to increase motivation for treatment
- 6) Review the following areas:
 - A. Monitoring and managing symptoms:
 - Review importance of buprenorphine adherence in managing cravings and preventing relapse.
 - Help identify cravings and warning signs of relapse
 - B. Patient education and self-management:
 - Educate about addiction and role of buprenorphine.
 - Review relapse prevention skills to cope with high-risk situations, cravings, and negative emotions

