ISTOP intervention group: The intervention arm will include in-hospital and post-discharge components (**Table 2**). Both components will be adapted from the MISSION-VET manual⁶⁸ under supervision from the mentors to be used for the ISTOP treatment manual. The candidate and recovery coaches will meet weekly to review all participants in the study. If the participant is re-hospitalized during the study period, the team will remain engaged with the patient, and the in-hospital component of the intervention repeated if the hospitalization occurs at BWH or BWFH.

In hospital component: There will be 2 sessions during the hospitalization, unless the patient is being discharged imminently, in which case both sessions will be completed at the same time (**Table 2**). Due to the COVID-19 pandemic, all recovery coach visits (both “in-hospital” and post-discharge) will occur remotely (either via phone or Partners Enterprise Zoom) until further notice. During the first session, the recovery coach will review goals of the intervention, complete a psychosocial needs assessment, and create a provisional treatment plan based on identified service needs. Following initiation of buprenorphine or methadone, the addiction social worker will provide the participant with the intake numbers for the BWH-affiliated buprenorphine programs and contact information for any relevant methadone programs. Patient preference due to geographic considerations will be taken into account when choosing the clinic to which participants are referred. The participants will be encouraged to schedule an appointment prior to discharge. The importance of continuing treatment will be reinforced. The recovery coach will focus on monitoring and managing symptoms, educate about the nature of recovery and relapse prevention skills, and reinforce the importance of community and social supports. The MISSION-VET manual, which covers the above elements, will be used to manualize the recovery coach intervention while in the hospital.⁶⁸ During the second session, the Recovery Coach will review the treatment plan, organize post-discharge appointments, reconcile medications, and provide naloxone rescue training. If applicable, family members will be encouraged to be present for all in-hospital sessions.

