Post-discharge component: Following discharge, the recovery coach will meet with the participant up to 3 hours per week (**Table 2**). Each recovery coach will carry a caseload of no more than 3 participants at a time. More frequent contact will be permissible if the care team needs to respond to emergencies or other clinical issues requiring additional contacts. For participants who may live outside of Boston or are otherwise unable to return to the Brigham Hospital area, the recovery coach will meet with participants via phone call or video conferencing. Each week, the coaches will conduct peer-led individual sessions using topics adapted from the MISSION-VET manual. The recovery coaches will encourage the continuation of treatment and accompany participants to appointments if necessary, and function as a liaison between the participant and the clinicians. The coaches will help determine recovery goals, share and suggest coping strategies, and model healthy living. The coaches will also instill hope through example, and provide support during crises. The coaches will assist with linkage to community programs, and assist with essential life skills such as setting up a bank account or using public transportation. The candidate will meet

weekly with the recovery coaches to review each case. If the participant successfully linked with the BWH-affiliated buprenorphine clinic, retention in treatment will be confirmed with the clinic.

Fidelity: The MISSION Fidelity Index from the MISSION-VET manual⁶⁸ will be adapted for this study to ensure intervention fidelity. The index is designed to document services delivered as indicated in the manual.

Compensation: Participants will be reimbursed \$50 for the baseline, 4- and 12-week follow-up visit, and \$100 for the 24-week visit.

Schedule of Assessments: Baseline measures will be obtained during the hospitalization. Follow up assessments will occur at 4, 12 and 24 weeks after discharge. A research assistant blinded to study assignment will collect all data. Patients who are unable to return to the hospital for the follow-up assessments will complete their measures via phone call or Partners Enterprise Zoom (if participant prefers) with the research assistant.

Measures: As recommended by notice NOT-DA-12-008, measures from the Substance Abuse and Addiction Collection of the PhenX Toolkit were chosen where appropriate. The schedule of assessments is summarized in **Table 3**.

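### Two stated procedures conflict with the promise of blinded data collection: the research assistant randomizes and takes baseline on the remote route, and a coach-specific questionnaire falls on every outcome visit

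*Combined protocol and SAP*

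**What the plan says.** **The commitment.** Section V, Schedule of Assessments: "A research assistant blinded to study assignment will collect all data". No visit and no questionnaire is excepted. Participants who cannot come back to the hospital will "complete their measures via phone call or Partners Enterprise Zoom (if participant prefers) with the research assistant".

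**The remote route.** Section IV: because of the pandemic, "we also propose an option for remote consenting for the duration of the public health emergency". The reason given is that "the research assistant will only be allowed on-site for a limited number of days each week". On this route the assistant telephones the participant, holds the consent discussion, and is to "then subsequently randomize the participant and conduct the baseline measures remotely via phone".

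**Allocation.** Section V, Randomization: "After informed consent is given, participants will be randomized using a computerized random number generator with numbers in sealed envelopes in study binders". The person who opens the envelope is not named. On timing, the Schedule of Assessments says only that "Baseline measures will be obtained during the hospitalization", so the in-person order of baseline and allocation is not stated.

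**The HCCQ-RC.** The Measures list in section V describes a 15-item form on how far participants feel their recovery coach supports their autonomy. Table 3 marks it at baseline and at weeks 4, 12 and 24, without restriction to one arm. Controls receive treatment as usual and have no coach.

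**Use of the data.** Under section VI, illicit opioid use (Hypothesis 1b) comes from the TLFB and urine toxicology, with baseline use as a covariate. Readmission (Hypothesis 2) comes from ASI and GAIN items. Retention (Hypothesis 1a) comes from the affiliated clinics.

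**The concern.** Participants in a coaching trial know their arm, and nothing can change that. Blinding the interviewer is the remaining protection for outcomes that depend on questioning and coding, and this plan claims that protection for all data. A reader of the results would rely on the claim when judging the TLFB and readmission comparisons.

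The procedures appear to give the arm away at two points. The first is enrollment on the remote route, where one role handles the allocation and takes the baseline interview. The second is every scheduled visit, where a form that makes sense in only one arm sits beside the TLFB and ASI. An interviewer who knows the arm may probe or code differently, without intending to.

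**Working it through.** The check is mainly a comparison of passages. The arithmetic only counts how often the second problem arises.

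**1. Remote route against the commitment**

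- The Schedule of Assessments has a blinded assistant collecting all data, and baseline data are part of that.
- Section IV gives the research assistant consent, randomization and baseline, listed in that order.
- The Randomization paragraph names no separate person to open the envelope and no means of hiding the result from the data collector.
- On the natural reading, then, remote baseline data are taken after allocation by someone who has handled it. Baseline illicit opioid use is among those data.
- This reaches follow-up only if the same assistant does the follow-up interviews. Both sections refer to the research assistant in the singular, but the number of assistants is not given.
- The share of participants enrolled remotely is not stated and could be anything from 0% to 100%.

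**2. HCCQ-RC against the commitment**

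Marks in Table 3:

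| Measure | Baseline | Wk 4 | Wk 12 | Wk 24 |
|---|---|---|---|---|
| TLFB | X | X | X | X |
| ASI | X | X | X | X |
| HCCQ-RC | X | X | X | X |

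- The HCCQ-RC falls on all 4 visits that carry the TLFB and ASI. It is 1 of 11 measures at baseline (10 others) and 1 of 9 at each follow-up visit (8 others).
- The documents do not make it self-completed, assign it to other staff, or place it after the outcome interviews. If the all-data sentence is followed, the blinded assistant either gives the form or skips it, and either act shows the arm.
- Weeks 4 and 12 precede the 24-week outcome interview, so the arm could be known by then even if the baseline mark is disregarded.
- The baseline form cannot be answered before allocation, because no participant yet has a coach. Leaving it at baseline therefore works against taking baseline first.

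**3. How many forms**

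- The plan's own sample size: 145 × (1 − 0.60) = 58 for analysis, and 58 / 2 = 29 per arm. The unpooled two-proportion formula for 40% against 10% agrees: (1.960 + 0.842)² × (0.4 × 0.6 + 0.1 × 0.9) / 0.3² = 28.8, rounded up to 29. Nothing in this point alters that figure.
- With 29 in the intervention arm and no attrition: 29 × 3 = 87 forms at follow-up, of which 29 × 2 = 58 fall at weeks 4 and 12.
- The Project Timeline implies 2 × 30 = 60 enrolled. With 30 per arm the counts become 30 × 3 = 90 and 30 × 2 = 60.
- None of these forms applies to a control participant.

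These are counts of opportunities, not a measure of bias. The documents give no input from which a shift in TLFB days or in reported readmission could be calculated.

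**4. Which outcomes are exposed**

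- TLFB days: most exposed, since the count is built up in an interview.
- Readmission from the ASI: less exposed, since it is analysed as a discrete event.
- Urine toxicology: obtained at routine clinical visits, outside the assessor's contacts.
- Retention: supplied by the clinics, so largely unaffected.

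**The case against.** **There may be more than one assistant.** The blinded assistant need not be the one who recruits. This stands, and it is why carry-over from the remote route to follow-up is only conditional. It does not remove the conflict at baseline, and it does not touch the HCCQ-RC.

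**The order is inferred.** The sentence in section IV joins randomizing and baseline with a simple conjunction, which does not strictly fix their sequence. This also stands: allocation before baseline is the natural reading, not the only one.

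**The plan foresees unmasked staff.** Section IX mentions an unmasked team member, but only for preparing the Closed Safety Report. That covers neither allocation nor the questionnaire.

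**On the HCCQ-RC the plan is silent rather than contradictory.** Mode of completion is indeed unstated. But the all-data sentence, together with remote follow-up measures taken with the assistant, points to the assessor unless something else is written.

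**Table 3 may have been damaged in text extraction.** The treatment-verification row is blank. The HCCQ-RC row, however, shows the same four marks as the TLFB and ASI rows.

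**GAIN items are in no visit schedule.** Correct. They appear only in the analysis section, so the point is limited to the ASI as the scheduled source of readmission data.

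**Participants know their arm, and the plan concedes that non-specific effects are uncontrolled.** True, but the interviewer's knowledge is a separate and avoidable source of bias, and the plan claims to have dealt with it.

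A reader might infer that follow-up assessment is shown to be unblinded throughout, or that the powered retention comparison is compromised. The documents support neither. Staffing and mode of completion are not stated, and retention comes from clinic data.

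**Conclusion.** As written, the procedures do not secure blinded collection of all data. The conflict is firmest for baseline interviews on the remote route, an optional and time-limited path of unknown uptake. The wider issue is the HCCQ-RC, which does not depend on that route and recurs at every TLFB and ASI visit.

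The conclusion rests on two assumptions: that the assistant who randomizes learns the allocation, and that the all-data sentence includes the HCCQ-RC. Both are natural readings, but neither is spelled out. The consequence is confined to the interview-based parts of Hypotheses 1b and 2. No size of bias or false-positive rate can be given; any such figure would need an assumed shift that the documents do not supply. The point is worth correcting because the correction is simple, not because the powered comparison is in doubt.

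**What to change.** 1. On both routes, complete the baseline measures (the 10 in Table 3 other than the HCCQ-RC) before the allocation envelope is opened.
2. Have the envelope opened by an existing team member who does not assess outcomes. Knowledge of the arm already exists in the team outside the blinded assistant: "The candidate and recovery coaches will meet weekly to review all participants in the study".
3. Delete the HCCQ-RC from the baseline visit.
4. Have the HCCQ-RC at weeks 4, 12 and 24 self-completed, or collected outside the assessor's interview by existing staff who are neither assessors nor coaches. The documents do not establish which staff are free, and eligibility requires only a working telephone, so the sponsor should choose the mode that fits.
5. Ask participants at each follow-up contact not to tell the assessor their arm.

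If this cannot be done, restrict the blinding statement so that it does not cover the TLFB and self-reported readmission outcomes.

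**Cost.** Wording changes in the schedule and operating procedures, a different order of steps at enrollment, and separate handling of about 87 to 90 short forms at most if attrition is nil and the arms are equal. Return of the HCCQ-RC may fall, but no stated hypothesis uses it. Sample size and planned analyses do not change.
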